COVER PAGE

Title of the study: Use of abdominal binder in colonoscopies performed by trainees in Gastrointestinal Endoscopy: A randomized, double-blind, sham-controlled trial

NCT number: NCT05617521

Document date: 01/29/2023

Study Protocol

Introduction

Colonoscopy is widely used for the diagnosis and treatment of colon diseases, and is also the preferred screening test for colorectal cancer (CRC) worldwide.^{1,2} The colonoscopy procedure is safe, well-tolerated, and accurate for examining the mucosa of the entire colon and distal terminal ileum. Nevertheless, it is technically demanding, even for the experienced endoscopists.³ One of the most frequent difficulties is the looping of the sigmoid and transverse colon. Looping stretches the colonic mesentery, leading to pain and discomfort in patients.⁴ Furthermore, looping prolongs the cecal intubation time (CIT), increases the number of incomplete procedures and the risk of associated complications, such as splenic injury and bowel perforation.^{5,6}

Ancillary maneuvers, such as abdominal pressure and patient position change, can be used to avoid the formation of the loops, but their effectiveness is questionable.⁷⁻⁹ The most used is the manual abdominal pressure, usually requiring to be exerted by an assistant, which may result in not effective uncontrolled compression.¹⁰ An abdominal binder is an alternative that seeks to improve the effectiveness of the abdominal pressure, encircling the abdomen to exert the pressure in an uniformly distributed way for the entire duration of the colonoscopy.¹¹

Several randomized controlled trials (RCTs) have evaluated the impact of abdominal compression devices during colonoscopy with contradictory results.¹¹⁻¹⁵ Two meta-analyses have revised these RCTs and both concluded that encircling abdominal devices reduces the CIT, the need for abdominal compression, and the frequency of postural change.^{16,17} Nevertheless, the limitations of both meta-analyses due to the reduced number of RCTs and them heterogeneity are remarkable. In addition, the colonoscopies in all RCTs studies were performed by experienced endoscopists, who would have less trouble managing loops and it would minimize any benefit using the abdominal binder.^{17,18}

This randomized trial was conducted to evaluate the effectiveness and safety of an abdominal binder use during colonoscopy performed by gastrointestinal endoscopy fellow trainees. We hypothesized that the abdominal binder use would facilitate and increase the effectiveness of the colonoscopy for inexperienced operators.

Methods

Trial design and population

It is a randomized, double-blind, sham-controlled study. The trial was performed at a single-center, Hospital Central Norte PEMEX, a tertiary center with a gastrointestinal endoscopy fellow trainee program with more than 10 years of experience. Outpatients between 20-80 years

scheduled for an elective colonoscopy were prospectively recruited for participation from November 2022 to January 2023. Inclusion criteria were patients with ingestion of the entire bowel preparation and categorized as American Society of Anesthesiologists Class (ASA) \leq III. Exclusion criteria were pregnancy, breastfeeding, multiple planned procedure, previous colorectal resection, history of intraabdominal malignancy, inflammatory bowel disease, liver cirrhosis or ascites, abdominal skin lesions, and anesthesia or analgesic allergy. This trial was conducted in accordance with the most recent version of the Declaration of Helsinki and approved by the local ethical committee. Written informed consent was obtained from all the patients before participation. This manuscript is reported in accordance with CONSORT guidelines.¹⁹ All the authors had reviewed and approved the final manuscript.

Trial interventions and device description

Prior to the procedure, age, sex, height, weight, body mass index (BMI), and colonoscopy indication of all participants were recorded. Once enrolled, patients were randomized to either the abdominal binder (AB) group or the sham binder (SB) group in a 1:1 ratio. Randomization was performed using a web-based computer system (Research Randomizer, Geoffrey C. Urbaniak and Scott Plous) by an independent statistician who had no other intervention in the study. An independent operator printed the randomization number and group for each participant (either the AB or SB group) in individual cards, which were hidden in a locked black box by the same independent operator. Only the nurse, who fitted the abdominal binder to all the patients in a private space, had access to the cards. Randomized data and cards were concealed to study coordinators, endoscopists, clinical staff, and participants.

The abdominal binder used for the patients allocated in the AB group was the Revive 3-in-1 Postpartum Recovery Support Belt (KeaBabies® Co., CA, USA). Its price is \$29.96. The device is manufactured in two size, One Size and X-Large. For the patients with a waist circumference >110 cm it was used the X-Large model. The three belts that make up the binder were fitted to all the participants. Once placed, the binder was adjusted to be located between the subcostal border and the anterior superior iliac spine. The participants were asked to confirm that the binder was fastened tightly but not uncomfortably. For the participants in the SB group the same binder was fitted, but once the patient was sedated, it was loosened by the same nurse. The participants wore a non-transparent gown over the binder so that it was not visible to the endoscopists.

Colonoscopy procedure details

Bowel preparation with 4 L of polyethylene glycol solution in split-dose (2 L at the afternoon of the day before and 5 h before the colonoscopy) was used in all the participants.²⁰ In this trial, all colonoscopy procedure were performed by two second-year fellow trainees in gastrointestinal endoscopy with 32 and 38 registered colonoscopies previous to the study.

A standard video-colonoscope (EC-3890Li, PENTAX Co., Tokyo, Japan) was used. All the patients were placed in the left lateral decubitus position. Sedation with propofol and fentanyl was initially performed in most cases, adding dexmedetomidine in one case. Then, the colonoscopy was started using standard maneuvers. Manual abdominal compression and postural change were conducted by a technician when required by the endoscopy trainee or the attending endoscopist. Endoscopist or anesthesiology were allowed to remove the binder at any time during the procedure if they resolve it was necessary for safety. Air insufflation was used during colonoscopy.

Outcomes

Primary outcome of this study was CIT (the time from the scope insertion to intubation of the cecum and visualization of the appendiceal orifice and ileocecal valvule). Main secondary outcomes were the cecal intubation length (CIL), ileocecal valve intubation time (IVIT), manual abdominal compression or postural change requirement, and the need for intervention by the attending endoscopist during the procedure. Other secondary outcomes included colonoscopy completion rate, trainee-reported insertion difficulty, adenoma detection, need for extra analgesic drugs, patient-reported pain, and satisfaction level at discharge of the endoscopy area. Before to leave the recovery room, the patients were asked for pain using a 10-point visual analog scale (VAS), and for satisfaction using a 5-point scale (5= very satisfactory, 4= satisfactory, 3= unsatisfactory, 2= very unsatisfactory, 1= extremely unsatisfactory) by an assistant blinded to the study.

Planned *a priori* subgroup analyses included stratification according to age, gender, and BMI. Participants with incomplete colonoscopy were excluded from the primary outcome analysis (CIT) and two of the main secondary outcomes (CIL and IVIT) yet included for the rest of the secondary outcomes. Primary analysis method was intention-to-treat (ITT), including all randomized participants. A per-protocol (PP) analysis method was also performed, excluding participants in the AB group whose binder was removed or loosened at any time of the procedure.

Bibliography

3. Shahidi N, Ou G, Telford J, Enns R. Establishing the learning curve for achieving competency in

performing colonoscopy: A systematic review. *Gastrointest Endosc* [Internet]. 2014;80(3):410–6. Available from: <http://dx.doi.org/10.1016/j.gie.2014.04.056>

4. Cheng W Bin, Moser MAJ, Kanagaratnam S, Zhang WJ. Analysis of and mathematical model insight into loop formation in colonoscopy. *Proc Inst Mech Eng Part H J Eng Med*. 2012;226(11):858–67.

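### Scheduled binder handling after sedation is described only in the sham arm, and the binder is not equalised before waking, so the double-blind is not protected against these two routes

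*Protocol*

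**What the plan says.** Protocol, Trial design and population: "It is a randomized, double-blind, sham-controlled study".

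Protocol, Trial interventions and device description:
- On who should not know the arm: "Randomized data and cards were concealed to study coordinators, endoscopists, clinical staff, and participants".
- On who does know it: "Only the nurse, who fitted the abdominal binder to all the patients in a private space, had access to the cards".
- On the fit, with no restriction by arm: "The participants were asked to confirm that the binder was fastened tightly but not uncomfortably".
- On the sham, which starts with an identical binder: "once the patient was sedated, it was loosened by the same nurse".
- An opaque gown is worn to keep the binder out of the endoscopists' sight.

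Protocol, Colonoscopy procedure details: a technician performs compression and position change when the trainee or attending asks. The endoscopist or anesthesiology may take the binder off for safety at any time, in either arm.

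Protocol, Outcomes: the secondary outcomes include these maneuvers, intervention by the attending, trainee-reported difficulty and "need for extra analgesic drugs". Pain and satisfaction come last: "Before to leave the recovery room, the patients were asked for pain", and satisfaction is asked at the same time, by a blinded assistant.

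Neither document describes AB handling to match the loosening, where the loosening took place, who was there, the state of the binder at waking, or a check of blinding.

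**The concern.** A sham protects the comparison only if the people who make decisions or give ratings see the same thing in both arms. Here the step that creates the sham is itself a difference between the arms, and it comes after the patient has left the stage that the protocol places in private.

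There are two routes to the allocation. In the room, anyone who watches the nurse loosen the binder can infer that the patient is SB. At waking, an SB patient who earlier confirmed a tight fit may find the binder loose before rating pain and satisfaction.

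At stake are outcomes that someone in the room decides or rates, and two that the patient rates. If a trainee or attending believes the patient has no support, the threshold for asking for compression, or for stepping in, may shift. The arms could then differ for reasons other than the binder.

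**Working it through.** The point is one of procedure, so the main check sets the stated safeguards against the two routes.

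1. **Scheduled handling after sedation.** SB: loosening by the nurse. AB: none described. With 1:1 allocation and 206 patients (SAP), that is 103 patients with the scheduled act and 103 without.

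2. **Does any safeguard cover the act in the room?**
   - Private space: stated for the fitting. The loosening comes later, after sedation, and its place is not given.
   - Gown: stated to hide the binder from the endoscopists. It does not hide a nurse loosening the binder, and its stated purpose does not extend to sedation staff or the technician, who fall under the clinical staff meant to be blinded.
   - Concealed cards: these protect the written allocation, not an arm inferred from what is seen.

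   None covers it.

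3. **Does any safeguard cover waking?** The blinded assistant protects the person asking. The patient gives the rating, and no step re-tightens or removes the binder in both arms beforehand. None covers it.

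4. **Which outcomes are exposed?** The Outcomes section lists 11, counting compression or position change as one.
   - Staff decisions or ratings (four): maneuvers, attending intervention, trainee-rated difficulty, extra analgesics.
   - Patient ratings (two): pain, satisfaction.
   - CIT: reached only through maneuvers and attending intervention. A difficulty rating cannot alter the time it describes. Only incomplete colonoscopies are excluded from CIT, so under the stated rule completed procedures with attending help remain in. More maneuvers or earlier help in SB could change SB CIT either way.

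5. **Could the sample size absorb the problem?** First the SAP's own figure, with difference 60 s, SD 110 s, 90% power and two-sided alpha 0.05:
   - n per arm = 2 × (1.960 + 1.282)² × 110² / 60² = 70.6, rounded up to 71, so 142 in total, as the SAP states.
   - At 103 per arm the standard error is 110 × √(2/103) = 15.3 s. Then 60/15.3 − 1.96 = 1.95, which gives power of about 97%.

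   Power is ample. A bias from unblinding does not shrink as n grows, so sample size is no remedy.

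**The case against.** The strongest reply is that silence is not evidence. The protocol does not say where the loosening was done or who could see it, and it does state real safeguards: locked cards, one unblinded nurse, private fitting, an opaque gown and a blinded assistant. The waking route also needs several conditions: the SB patient still wears the binder when alert, notices that it is loose, and takes loose to mean sham. The documents do not settle these.

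This stands as a limit on the conclusion. A reader might infer that the trial was in fact unblinded, or that the handling identifies the arm with certainty. The documents support neither. Safety removal is allowed in either arm, and the per-protocol rule foresees AB binders being removed or loosened, so the contrast holds for scheduled handling only.

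A reader might also put a figure on the bias, or say that most outcomes rest on staff judgment. No figure can be derived, and staff judgment directly determines four of the 11 listed outcomes.

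The reply does not supply the missing protection. A team that followed the protocol to the letter would produce a cue in one arm only, with nothing in the text to mask it.

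**Conclusion.** The point holds in limited form. The double-blind is not protected against two routes: sight of a scheduled act that occurs only in SB, and a binder that may be in a different state by arm when the patient wakes. Actual unblinding is an open risk.

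The cue is scheduled in all 103 SB patients and in no AB patient. How often it was seen, and what effect it had, cannot be estimated from the documents. Maneuvers, attending intervention, trainee-rated difficulty, extra analgesics, pain and satisfaction are most exposed. The primary outcome, CIT, is exposed only indirectly and the direction is unknown.

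The conclusion assumes that the protocol describes all scheduled handling of the binder. If matching AB handling, screening and a common binder state at waking were in fact used, stating so would resolve it.

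**What to change.** For a repeat of the trial, or any further recruitment:
- After sedation, the same nurse carries out handling of the same duration under the gown in every patient: real loosening in SB, and mock handling in AB that leaves the tension unchanged.
- This is done out of view of the trainee, attending and technician and, as far as possible, of sedation staff.
- The binder is brought to the same state in both arms (for example, removed) before the patient can notice its tightness and before pain and satisfaction are rated.

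The cost is a little nurse time per AB patient and a few sentences of protocol text. One limit remains: a technician pressing on the abdomen might still feel whether the binder is tight.

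The protocol reports recruitment from November 2022 to January 2023, so for the patients already treated the remedy is reporting. State who was present at the loosening, whether AB had mock handling, the binder state at waking by arm, and whether blinding was checked. If the matching steps were not taken, describe maneuvers, attending intervention, trainee-rated difficulty, extra analgesics, pain and satisfaction as not reliably blinded, and note the indirect exposure of CIT. This needs no new patient data.

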Statistical Analysis Plan

Use of abdominal binder in colonoscopies performed by trainees in
Gastrointestinal Endoscopy: A randomized, double-blind, sham-
controlled trial

NCT05617521

09/24/2023

Sample size was estimated over the primary outcome of the study based on pre-experimental data estimation and previously reported CIT and SD of similar studies with fellows' participation. It was calculated that 142 participants were needed to detect a 60-second difference in CIT (SD 110 sec), with 90% power and two-side alpha 0.05. Moreover, it was also calculated based on the frequency of ancillary maneuvers, using pre-experimental data estimation and literature data. It was found that 186 participants (93 per group) were needed to detect a 20% reduction in the use of ancillary maneuvers, with 90% power and two-side alpha 0.05. As a preventive measure in case of withdrawal or exclusion, the sample was expanded by 10%, a total of 206 patients, 103 in each group were included in the study.

Descriptive statistical analysis, including mean, mode, and frequencies will be performed for the description of the study data. The comparative analysis of the quantitative data will be previously subjected to normality evaluation by the Shapiro–Wilk test and graphical analyses. According to the normality, data comparative analysis will be performed either with a two-way Student's test or U Mann–Whitney test. For the comparative analyses of the categorical data (e.g., manual abdominal compression, postural change, need of intervention by the attending endoscopist) will be used chi-square or Fisher' exact test. A p value of <0.05 will be accepted as statistical significance. Statistical inferential analysis will be performed using RStudio® (R Core Team v.1.2.5033; R Foundation for Statistical Computing, Vienna, Austria) and SPSS® Statistics for Windows Version 23.0 (IBM Corp., Armonk, NY, USA). RStudio® (R Core Team v.1.2.5033) will be also used for drawing graphics. The study biostatistician (SA) will be blinded to the randomization phase and recollection data process.

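### The two trainees' combined experience rises about fourfold during the trial, but the CIT analysis has no term for trainee or case order and no look at the effect by operator experience

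*Protocol*

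**What the plan says.** - **Operators.** Protocol, Colonoscopy procedure details: all procedures are "performed by two second-year fellow trainees in gastrointestinal endoscopy with 32 and 38 registered colonoscopies previous to the study".
- **Rationale.** Protocol, Introduction: earlier trials used experienced endoscopists, "who would have less trouble managing loops and it would minimize any benefit using the abdominal binder". The objective follows: "We hypothesized that the abdominal binder use would facilitate and increase the effectiveness of the colonoscopy for inexperienced operators".
- **Allocation.** Protocol, Trial interventions and device description: "patients were randomized to either the abdominal binder (AB) group or the sham binder (SB) group in a 1:1 ratio". No stratification by trainee and no blocking over time is described.
- **Size.** SAP, sample size paragraph: "a total of 206 patients, 103 in each group were included in the study".
- **Analysis.** SAP, analysis paragraph: for quantitative outcomes, "data comparative analysis will be performed either with a two-way Student's test or U Mann–Whitney test". No covariate is named.
- **Subgroups.** Protocol, Outcomes: the a priori "subgroup analyses included stratification according to age, gender, and BMI". Operator experience is not among them.

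The documents do not give the split of cases between the trainees, a learning slope for CIT, or a case count at which an operator stops being inexperienced.

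**The concern.** The trial exists because the sponsor expects the binder to help less as operators become more skilled. Operator experience is therefore the effect modifier that the hypothesis rests on, and it changes a great deal between the first patient and the last. The plan examines three patient traits as modifiers but not this one.

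Three things are at stake. First, differences between the trainees and their improvement over time stay in the residual variance, so precision is lost. Second, if the benefit does fade, the pooled difference is smaller than the effect in early cases. A small or null result would then be hard to interpret, and a positive one could not be tied to a level of experience. Third, the report would say nothing about how the effect varies with experience, which is the question behind the trial.

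**Working it through.** **Inputs.** Prior counts 32 and 38 (Protocol, Colonoscopy procedure details). From the SAP sample size paragraph: 206 patients, 103 per arm, CIT difference 60 s, SD 110 s, 90% power, two-sided alpha 0.05. Everything marked *assumed* is not in the documents.

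**1. The plan's own figure.** The SAP states: "It was calculated that 142 participants were needed to detect a 60-second difference in CIT (SD 110 sec"). Per arm, n = 2 × (1.96 + 1.2816)² × 110² / 60² = 70.6, rounded up to 71, so 142 in total. The figure reproduces.

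**2. Rise in experience.**
- Combined: (70 + 206) / 70 = 276 / 70 = 3.94 times, whatever the split.
- Even split (*assumed*): 32 + 103 = 135 (4.2 times) and 38 + 103 = 141 (3.7 times).
- Splits from 30:70 to 70:30 (*assumed*): 2.9 to 5.5 times for the trainee starting at 32, and 4.8 to 2.6 times for the one starting at 38.

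Colonoscopies done outside the study would add to these counts.

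**3. Power of the pooled test.** SE = 110 × √(2/103) = 15.3 s. Power ≈ Φ(average effect / 15.33 − 1.96). Incomplete colonoscopies are excluded from CIT, so 103 per arm is an upper limit.

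| Average effect | Example of a pattern (*assumed*) | Power |
|---|---|---|
| 60 s | constant 60 s, or linear fade from 90 to 30 s | 97.5% |
| 45 s | linear fade from 60 to 30 s | 83.5% |
| 30 s | linear fade from 60 to 0 s | 50% |

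If the effect falls from 60 to 0 s in proportion to log experience (*assumed*), the average is about 23 s, with power between the 26% for 20 s and the 50% for 30 s.

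**4. What adjustment gains.** Suppose CIT falls linearly by L seconds over the trial (*assumed*) and total SD stays at 110 s. The learning share of the variance is (L²/12) / 110², and the adjusted SE is about 15.33 × √(1 − share).
- L = 120: share 1,200 / 12,100 = 9.9%, SE 14.6 s.
- L = 180: share 2,700 / 12,100 = 22.3%, SE 13.5 s.
- L = 240: share 4,800 / 12,100 = 39.7%, SE 11.9 s.

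Simulation with the terms actually fitted gives 14.6, 13.6 and 12.0 s. The SD of the chance-imbalance shift that adjustment removes is √(15.3² − 14.6²) = 4.6 s, √(15.3² − 13.6²) = 7.0 s and √(15.3² − 12.0²) = 9.5 s. This is the same gain in another form.

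Main-effect terms do not undo dilution. If they explain 10 to 30% of the variance (*assumed*), power for a 30 s average effect rises only from 50% to between 54% and 65%.

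**5. What an interaction could show.** With case order scaled 0 to 1 (variance about 0.085), the SE of the arm-by-case-order slope is 15.33 / √0.085 ≈ 53 s. Power for a 60-to-0 s fade is Φ(60/52.6 − 1.96) = Φ(−0.82) ≈ 21%, rising to about 31% with the 240 s learning fall. The SE of the effect at the first case is about √(15.33² + (0.5 × 52.6)²) ≈ 30 s, falling to about 24 s with the 240 s fall.

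**The case against.** The strongest reply is that the planned comparison already answers the stated question. The protocol evaluates colonoscopy by fellow trainees, every case qualifies, and no document says where inexperience ends. Randomization makes the unadjusted comparison valid for the average effect over these cases. This stands.

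A reader might infer that a benefit limited to inexperienced operators would be averaged away. The documents do not support that, for three reasons:
- Even a fade from 60 s to zero leaves a 30 s average and about 50% power, which is dilution and not disappearance.
- The Introduction says experience minimizes benefit, not that it abolishes it. It also reports two meta-analyses, of trials run entirely by experienced endoscopists, that found shorter CIT (while noting their limitations). Zero effect at about 140 cases, with both operators still trainees, is therefore not what the rationale implies.
- The SAP's 60 s is the between-arm mean difference the trial is sized to detect. Placing it at the first case only is an assumption; a fade from 90 to 30 s keeps full power.

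A reader might also count chance imbalance in trainee or early cases as a bias on top of the loss of precision. It is not, because it is already inside the 15.3 s SE.

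It can also be objected that the interaction is too imprecise to separate improving trainees from an ineffective binder. That is true, and it limits what the added analysis can claim. It does not justify leaving out the modifier the rationale names, when adjustment costs almost nothing.

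**Conclusion.** The point holds as a gap in precision and in information, not as a flaw in validity. The fourfold combined rise in experience follows from the documents, given that all 206 procedures are done by these two trainees. So does the absence of any trainee or case-order term, stratum or subgroup.

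The size of the consequence cannot be fixed from the documents. Power at 103 per arm runs from 97.5% to about 50% as the average effect goes from 60 to 30 s. The SE could fall from 15.3 s to between 14.6 and 12.0 s if CIT falls by 120 to 240 s over the trial. These figures rest on the SAP's SD of 110 s, a t-type comparison of means, and assumed linear patterns of learning and fading. The upper end of the gain needs learning to explain about 40% of the variance.

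**What to change.** Add to the SAP:

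1. A linear model for CIT (log CIT if skewed) with arm, trainee and case order within trainee, where case order is the prior count of 32 or 38 plus study cases so far. Declare it as an adjusted analysis beside the t or Mann–Whitney test. Label it with its date, because the SAP (09/24/2023) postdates recruitment (November 2022 to January 2023) and the analysis cannot be presented as a priori.
2. An exploratory arm-by-case-order term. Report the binder effect with 95% CI at low and high case number and by trainee, as estimates and not as tests.
3. A conclusion limited to two trainees over the observed range of experience, with the actual split of cases reported.

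**Cost.** SAP wording and one extra regression analysis, with no new patients or procedures. It assumes that operator and procedure date are on record for each case, which the documents do not state. Colonoscopies outside the study are not counted unless they were also logged. The named downside is imprecision: about 20 to 30% power for a 60-to-0 s fade, and a first-case SE of about 24 to 31 s. Stratifying the randomization is no longer possible and is not proposed.

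### Subgroups by age, gender and BMI are planned by stratification, but neither document includes a test of whether the binder effect differs between subgroups.

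*Protocol*

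**What the plan says.** The Outcomes section of the protocol states that the a priori "subgroup analyses included stratification according to age, gender, and BMI". It gives no cut-points for age or BMI, does not name the outcomes to be examined by subgroup, and does not say how a difference between subgroups would be judged.

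The SAP does not mention subgroups. For quantitative outcomes, "data comparative analysis will be performed either with a two-way Student's test or U Mann–Whitney test", depending on a normality check. For categorical outcomes the SAP says that there "will be used chi-square or Fisher' exact test". The threshold is general: "A p value of <0.05 will be accepted as statistical significance". Neither document contains an interaction test, a regression model or a multiplicity rule.

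**The concern.** A subgroup analysis asks whether the treatment effect differs between kinds of patient. A t-test, Mann-Whitney, chi-square or Fisher test within a stratum asks only whether the arms differ in that stratum. Halving the sample lowers power in each half, so two strata with the same true effect will quite often fall on opposite sides of p = 0.05. If that pattern is taken as evidence that the binder works in one group and not in the other, the claim rests on a comparison that never tested it.

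BMI is where this could matter most. The protocol's bibliography includes a compression-device trial whose title reports a benefit in some obese patients, so a BMI-specific result here would be taken seriously. The a priori label would lend it further weight.

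**Working it through.** **Inputs from the SAP.** 60 s difference in CIT, SD 110 s, two-sided alpha 0.05; 206 participants (103 per arm). The lower scenario is 186 (93 per arm), the SAP's figure before its 10% expansion. I use it because the protocol removes incomplete colonoscopies from the CIT analysis, so fewer than 206 may contribute.

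**Assumptions, because the documents are silent.** Two strata per factor, the splits shown below, the arms balanced within strata, and normal data. For the three-factor results, the factors are also independent of each other.

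**Step 1: the plan's own figure.** The SAP states that "142 participants were needed to detect a 60-second difference in CIT (SD 110 sec"), "with 90% power and two-side alpha 0.05". By the normal approximation, n per arm = 2 × (1.960 + 1.282)² × 110² / 60² = 70.6, rounded up to 71, or 142 in total. The stated figure reproduces.

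**Step 2: one factor, the same 60 s effect in everyone.** Power is from the noncentral t distribution. At 103 per arm, overall power is 97.4%. With powers p1 and p2 in the two strata, the chance that exactly one is significant is p1(1 − p2) + p2(1 − p1). Results are from unrounded powers.

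| N | Split | Per arm in each stratum | Power in each stratum | Exactly one significant |
|---|---|---|---|---|
| 206 | 50/50 | 51.5 / 51.5 | 78.3% / 78.3% | 34.0% |
| 206 | 30/70 | 30.9 / 72.1 | 55.9% / 90.2% | 45.2% |
| 206 | 20/80 | 20.6 / 82.4 | 40.1% / 93.6% | 58.7% |
| 186 | 50/50 | 46.5 / 46.5 | 74.0% / 74.0% | 38.5% |
| 186 | 30/70 | 27.9 / 65.1 | 51.6% / 87.0% | 48.8% |
| 186 | 20/80 | 18.6 / 74.4 | 36.6% / 91.1% | 61.0% |

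For the first row: 2 × 0.783 × 0.217 = 0.340. A smaller uniform effect does not help. At N = 206 and 50/50, effects of 50, 40 and 30 s give about 47%, 49% and 40%.

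**Step 3: three factors together.** The factors divide the same patients, so their results are correlated and the rates were simulated (20,000 trials, N = 206, three independent 50/50 factors).

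| Truth | Separate stratum tests | Interaction tests |
|---|---|---|
| Uniform 60 s effect | at least one of three factors discordant: about 56% | at least one of three false positives: about 14% |
| No effect | at least one of six strata significant: about 21% | at least one of three false positives: about 14% |

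The 14% agrees with 1 − 0.95³ = 0.143; each interaction test alone keeps about 5%.

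**Step 4: what an interaction test can detect.** With two equal strata at N = 206, the SE of the difference between stratum effects is 110 × √(4/51.5) = 30.7 s. For a true 60 s difference between strata, 60/30.7 = 1.96, so power is about 50%.

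**The case against.** The strongest objection is that the harmful step is not in the documents. The protocol has one sentence on subgroups, and the SAP does not tie its tests to strata. The strata might be reported as estimates only. This stands. A reader might infer that the plan commits the investigators to treating significance in one stratum but not the other as effect modification; the text does not say so. What remains is that the documents provide no other means of comparing subgroups and no rule of interpretation.

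A reader might also set the 56% or the 21% beside the interaction test's 5%. That comparison is uneven, because 5% is a rate per factor. Like for like, it is 56% against 14% under a uniform effect and 21% against 14% under no effect. The first gap is large, the second modest.

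Nor are the rates above the plan's own error rates. Cut-points, number of strata and splits are all unstated, so only a range under stated assumptions is justified.

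One might read the SAP's two-way Student's test as a two-factor model that could carry an interaction. It more plausibly means two-tailed, since it is offered as the alternative to a Mann-Whitney test.

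Finally, the three factors are named in advance and were recorded before the procedure, and the primary comparison does not depend on them. That is correct, and it limits the weight of the point.

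**Conclusion.** The concern holds in a conditional form. The plan announces subgroup analyses but includes nothing that tests whether the binder effect differs between subgroups. If stratum p-values are compared, a uniform 60 s effect would look subgroup-specific in about 34% to 59% of trials per factor at N = 206, and 39% to 61% at N = 186, across splits from 50/50 to 20/80. These figures rest on the SAP's effect and SD and on the assumptions of two strata per factor and normal data. More than two strata would lower the power in each further.

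This should be corrected, but it bears on secondary conclusions only. The primary CIT comparison and the sample size are unaffected.

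**What to change.** For each of the three named factors, add one treatment-by-subgroup interaction test: a linear model for CIT and a logistic model for ancillary maneuvers. State the cut-points and the outcomes. Fix the scale for CIT in advance (for example log, if it is skewed), because the presence of an interaction depends on the scale. Report the effect in each stratum with its 95% CI and omit the stratum p-values. Base any claim of a subgroup difference on the interaction alone, and label these analyses exploratory, since about 14% of trials would still show at least one false-positive interaction among three. Modelling age and BMI as continuous is an optional refinement and is not needed to close the gap.

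The cost is a few sentences in the SAP and one model term per factor and outcome, with no new patients or data. If outcome data have already been examined, the report should say that the cut-points and scale were set afterwards. The drawback is that fewer subgroup claims will be made. At about 50% power for a 60 s difference between equal strata, a non-significant interaction does not show that the effect is uniform, and the report should say this.
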